**9.7.1 Gestation at delivery for women having induction of labour**

**9.7.2 Gestation at delivery**

**9.7.3 Birthweight centile**

## **9.8 Baby outcomes**

The following will be presented and summarised by intervention and overall:

- Sex of baby
- Birthweight of baby
- Apgar score at 5 minutes
- Proportion of babies with 5 minute Apgar score < 4
- Proportion of babies with 5 minute Apgar score < 7
- Resuscitation required at birth

## **9.9 Process Outcomes**

The following outcomes will be obtained from the study team audit and presented and summarised by intervention and overall:

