3 STUDY DESIGN

This is a multicentre, stepped wedge cluster randomised trial of a package of care consisting of a management plan for identification and delivery of the 'at risk' fetus, together with strategies for increasing pregnant women's awareness of the need to report decreased fetal movements early. A nested qualitative study will examine the acceptability of the intervention to patients and health care providers and identify process issues (barriers to implementation). Clinical audit (before and after the change in practice) will be used to determine the effect of interventions on process outcomes (eg number of ultrasound scans, number of admissions for induction of labour). The study will take place in participating hospitals in the UK.

The interventions will be introduced over a 33 month period. Data will be collected over a 36 month period.

Data in the 'active phase' after introduction of the intervention will be compared to data in the 'control phase' – the time from study start to the time of introduction of the intervention. Given

that it will take individual units some time (a) to effect change in management in their unit from time of introduction of the intervention and (b) that it will take some time for this change in practice to impact on clinical outcomes, we plan a “washout” period after the introduction of the intervention during which data will not be included in either group for analysis. We anticipate that this washout period will be of two months duration – this will be finalised in the statistical analysis plan.

Outcomes will be measured from routinely collected data. For consistency, we will normally only include data items which become available within four months after the delivery date in question, although we may seek advice from the TSC about exceptions as they arise.

A diagram indicating randomisation of hospital groupings in the stepped wedge design is shown below:

Table 1: Stepped wedge design. Shaded areas indicate periods in which the interventions are being implemented. The order in which hospital groupings implement the interventions will be determined via randomization.

Hospital groupings	Month								
	1-4	5-8	9-12	13-16	17-20	21-24	25-28	29-32	33-36
1-3									
4-6									
7-9									
10-12									
13-15									
16-18									
19-21									
22-24									

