8.2 PROPOSED ANALYSES

For the binary outcomes being addressed in research questions Q1-Q4, data will be analysed by generalized linear mixed model with a random effect for hospital group and fixed effects for the intervention implementation and study time period. Data will be analysed on an intention to treat basis (the design of the trial means it is not possible to determine individual patient /caregiver compliance with the intervention). There will be no imputations for missing data. Subgroup analyses will include those with and without congenital anomalies. No interim analyses will be performed other than those requested by the trial steering committee, who will be the only group to view the interim analyses. A full statistical analysis plan will be developed and signed off prior to locking of the study database.

For research question Q5, the qualitative data will be audio recorded and transcribed. The data will be coded thematically and an analytical framework developed to make sense of patient experience of fetal movement and the intervention and also health care providers’ perspectives and experiences. NVivo will be utilised to support the analysis. The RA and [name] will work together to ensure rigour and validity.

The process outcomes being assessed in Q6 (rates of induction of labour, number of women presenting with decreased fetal movements, interval between perceiving fetal movements and presenting to hospital) will be analysed using the same methods as for Q1-Q4, with the exception of the continuous outcome (interval between perceiving fetal movements and presenting to hospital) which will be analysed in a normal linear mixed model.

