As always, thank you so much for your help with AFFIRM.

Best Wishes

[name] and [name]
On behalf of the AFFIRM Study

NB: If you wish to print and fax your completed sheet to us, the number is [name]

B) **CLINICAL AUDIT** to determine whether the perception of the site Principal Investigator is supported by review of actual decision making will be performed for the following elements:

- Cardiocography within 2 hours of presentation,
- Measurement of amniotic fluid volume within 12 hours of presentation,
- Growth scan by the next working day for all women presenting with reduced fetal movement (and who had not had a growth scan within the last three weeks, or who were not being induced within 48 hours),
- Induction of labour within 48 hours for women presenting with recurrent reduced fetal movement at or after 37 weeks gestation.

This will be conducted by asking sites to complete an audit of the management of all women presenting with reduced fetal movement over the course of one calendar month. Sites will be asked to complete an audit form for each participant.

The audit form template (see below) has been generated by the central AFFIRM study team; anonymized forms will be analysed centrally. There will not be an attempt to corroborate Principal Investigator perception of the proportion of women who were given leaflets, nor will there be any attempt to incorporate the proportion of staff who had completed the e-learning package into analysis of whether any specific site has implemented the intervention or not.

AUDIT PART B: CLINICAL AUDIT FORM - One month data collection AUDIT [Month & Year] Unit name: [Name of Hospital]

If you assess a woman with reduced fetal movements (RFM), please complete the questions below. Do not worry if the woman has been seen in other areas of the hospital by other staff, we would rather have multiple reports for the same woman than miss episodes of RFM.

INSERT Patient Sticker (or WRITE name and CHI /NHS number)				AREA WHERE SEEN (CIRCLE)						
				Triage / Labour ward / Day Assessment Unit (DAU)						
				Other (specify area i.e. antenatal ward): _____						
Date and time of presentation with reduced fetal movements.	DATE: ____/____/____ TIME ____:____ am / pm			GESTATION AND EDD:	____ WEEKS ____ DAYS EDD: _____					
Referred by (TICK BOX):	Self	Community Midwife	GP	ANC	Triage	DAU	Other (specify: _____)			

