What was the primary reason for attending/phoning? (TICK BOX):	Reduced Fetal Movements			Other (specify: _____)						
How many times has the woman attended before this visit, with RFM? (TICK BOX):	None – first attendance		Once previously	Unknown	Multiple times (please provide the gestation at each presentation i.e. 30+6)	1	2	3	4	5
What was the time interval from the woman first being aware of reduced fetal movements and attending the hospital (in hours)?					HOURS: _____					
Has she been given a leaflet "Your baby's movements in pregnancy"? (TICK BOX):	Yes – she already has one		Yes – I have given one to her today		Locally Created Leaflet Given			NO		
Has this woman had a growth USS in this pregnancy? (TICK BOX):	No, she has not had a growth scan		Yes, within the last 3 weeks (date of scan): DATE: ____/____/____		Yes, but more than 3 weeks ago (date of scan): DATE: ____/____/____					

Can Promoting **A**wareness of **F**etal movements and **F**ocussing **I**nterventions **R**educe **F**etal **M**ortality - a stepped wedge cluster randomised trial? **AFFIRM**

CONTINUATION: NHS/ CHI NUMBER:

Are any of the following risk factors for Fetal growth restriction present (CIRCLE all that apply)?							
Age ≥40 or ≤16	Smoker ≥20cpd	Known or suspected growth restriction	Congenital anomaly	Raised BP (essential hypertension, pre-eclampsia or pregnancy induced hypertension)	Previous pre-eclampsia	Diabetes or gestational diabetes	Previous FGR or stillbirth
What investigations were conducted during this episode of reduced fetal movement?							
Please record below the date and time that these investigations were completed or indicate if not performed.					Please provide the results (CIRCLE):		
CTG	Not performed		DATE: __/__/____	TIME: ____:____ am/pm	Normal / Suspicious / Pathological		
					Computerised CTG: YES / NO (CIRCLE)		
Liquor volume assessment on scan	Not performed		DATE: __/__/____	TIME: ____:____ am/pm	Normal / Reduced / Increased		
Growth scan	Not performed		DATE: __/__/____	TIME: ____:____ am/pm	Normal / EFW < 10 th centile / AC < 10 th centile / EFW and AC < 10 th centile		
Umbilical Artery Doppler	Not performed		DATE: __/__/____	TIME: ____:____ am/pm	Normal / > 95 th centile / absent EDF / reversed EDF		
MCA Doppler	Not performed		DATE: __/__/____	TIME: ____:____ am/pm	Normal / < 5 th centile		
DELIVERY METHOD (If available)							

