### 5.3 Process outcomes:

These will be recorded in a subset of sites and women via clinical audit.

- Number of women presenting with decreased fetal movements
- Interval between perceiving decreased fetal movements and presenting to hospital

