### **9.2 Demographics, Clinical Characteristics**

No formal statistical testing will be performed for demographics and clinical characteristics. The following will be presented and summarised by intervention and overall:

Maternal parameters:

- Mother's age at delivery (years)
- Mother's height (cm)
- Mother's weight at booking (kg)
- Maternal BMI
- Ethnic group
- Smoker during pregnancy
- Smoking history at booking
- Deciles of deprivation (Scotland Only)
- Parity

- Number of births this pregnancy
- Mode of Delivery

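### SAP 9.9 replaces the protocol's mixed models for two audit process outcomes with phase summaries and gives no reason; separately, SAP 9.8 could cheaply time-adjust three binary baby outcomes

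*SAP*

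**What the plan says.** **Process outcomes.** Protocol 8.2 lists three outcomes under Q6: induction of labour, number of women presenting with decreased fetal movements, and interval to presentation. It says they "will be analysed using the same methods as for Q1-Q4, with the exception of the continuous outcome", which gets a normal linear mixed model. The Q1-Q4 method has a random hospital-group effect and fixed effects for intervention and time period. SAP 6 reproduces this text. Protocol 3 gives the purpose of the audit: "Clinical audit (before and after the change in practice) will be used to determine the effect of interventions on process outcomes".

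For number presenting and interval, SAP 9.9 says: "The following outcomes will be obtained from the study team audit and presented and summarised by intervention and overall". It gives no model, period effect or effect estimate. SAP 5.3 says of the same outcomes: "These will be recorded in a subset of sites and women via clinical audit". Induction of labour is still modelled, in SAP 9.6.7.

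**Baby outcomes.** SAP 5.2 lists Apgar below 4, Apgar below 7 and resuscitation among the secondary baby parameters. SAP 9.8 presents them by intervention and overall only. From the same list, preterm birth (9.6.16), gestation (9.7.2) and birthweight centile (9.7.3) are modelled with study-period effects.

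**The concern.** In this design every site moves from control to active and never back, so active births are later births. A crude comparison by phase mixes the intervention with whatever else changed over the three years. The period effect in the planned models deals with this, and SAP 9.8 and 9.9 leave it out.

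For SAP 9.9 this also departs from the protocol. Whether women present more often or sooner belongs to secondary objective Q6, and earlier presentation is part of the protocol's account of how the package might work (section 1.1). Under SAP 9.9 that question has no time-adjusted answer, and a reader is not told that the protocol's analysis was set aside. For SAP 9.8, crude Apgar and resuscitation tables would sit beside period-adjusted results, and a secular trend could be read as benefit or harm.

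**Working it through.** **Process outcomes: comparison of texts**

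| Q6 outcome | Protocol 8.2 | SAP section 9 |
|---|---|---|
| Induction of labour | Q1-Q4 mixed model | Modelled (9.6.7) |
| Number presenting | Q1-Q4 mixed model | Summary by phase (9.9) |
| Interval to presentation | Normal linear mixed model | Summary by phase (9.9) |

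Neither SAP 9.9 nor the SAP version history explains the second and third rows. The protocol's own text has a gap too. Its Q1-Q4 model is for binary outcomes, and no denominator is given that would turn a number of women into a proportion or rate.

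**Baby outcomes: calendar imbalance**

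Inputs: 58,000 + 50,000 = 108,000 births a year, 24 groups and three groups stepping every four months (protocol 8.1); a two-month washout (SAP 4.1); 36 months of data (protocol 3). Births are assumed equal across groups and months.

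- Births per group-month: 108,000 / 12 / 24 = 375.
- A group at step k (k = 1 to 8) is in control from month 0 to 4k, and active from 4k + 2 to 36.
- Control: 3 × Σ4k = 3 × 144 = 432 group-months, so 432 × 375 = 162,000 births.
- Active: 3 × Σ(34 − 4k) = 3 × 128 = 384 group-months, so 384 × 375 = 144,000 births.
- Total: 306,000, which agrees with the figure of around 300,000 in protocol 4.1.
- Mean control month: Σ(4k)²/2 ÷ 144 = 1,632 / 144 = 11.3.
- Mean active month: Σ[36² − (4k + 2)²]/2 ÷ 128 = 3,248 / 128 = 25.4.
- Gap: 25.375 − 11.333 = 14.0 months.

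The documents give no trend for these outcomes, so a range is assumed. With no intervention effect, the crude active-to-control ratio is close to (1 + annual trend)^(14.04/12):

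| Assumed trend per year | Crude ratio |
|---|---|
| −5% | 0.94 |
| +5% | 1.06 |
| +10% | 1.12 |

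Averaging the trend over the actual birth months gives the same values to two decimals.

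Fitting nine period effects and a random group effect to the same trends, by generalised least squares on log rates, returns ratios of 0.998 to 1.003. The period effect therefore removes almost all of the distortion. The standard error of the adjusted log ratio is about 1.4 to 1.8 times the naive crude one, for assumed event rates of 0.3% to 10% and between-group coefficients of variation of 0.1 to 0.333.

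No such calculation is offered for SAP 9.9, because the audited sites and months are not stated.

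**The case against.** **A subset audit may support only description.** This is fair. SAP 5.3 points that way, and a small audit may say little however it is analysed. But the SAP does not offer this as its reason, while protocol 3 says the audit is there to determine an effect. What stands is that description may be the right outcome, provided the departure is declared.

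**SAP 9.8 is a legitimate choice.** This also stands. Protocol 8.2 names models for the binary outcomes of Q1-Q4 and for Q6. Apgar and resuscitation belong to neither, so a reader who inferred a protocol breach would be wrong. Neonatal harm already has period-adjusted analyses: perinatal mortality, three neonatal-unit admission outcomes and preterm birth. Birthweight and the Apgar score itself are descriptive in 9.8 too. The three binary outcomes are singled out only because they fit the existing model list without further specification.

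**Nobody would read a test into these tables.** Largely true. No test is planned in 9.8 or 9.9, and their wording is descriptive. Only SAP 9.2 says it outright: "No formal statistical testing will be performed for demographics and clinical characteristics". Similar words would help in 9.8 and 9.9, but their absence is not an error.

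**Two stronger readings of the audit are tempting.** A reader might take Appendix 5 as the source for SAP 9.9, because it asks for an "audit of the management of all women presenting with reduced fetal movement over the course of one calendar month" and its form records the interval ("What was the time interval from the woman first being aware of reduced fetal movements and attending the hospital (in hours"), and conclude that no control-phase data exist. Appendix 5 is headed as a compliance audit and is not stated to be that source, while protocol 3 describes an audit before and after the change. A reader might also infer that intervention and time cannot be separated in the audit at all. That result needs an assumed schedule and fixed site effects. The documents give no schedule, and they plan a random group or site effect.

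**Conclusion.** The discrepancy between protocol 8.2 and SAP 9.9 is real and rests on the text alone. Two of the three Q6 outcomes lose their planned model without explanation. Its numerical consequence cannot be stated, because the documents do not give the audit schedule.

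The SAP 9.8 part is an improvement, not an error. The 14-month gap follows from the planned design with equal births per month. The crude ratios of 0.94 to 1.12 also depend on the assumed trends of −5% to +10% per year, and would be nearer 1 if trends were flatter.

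No Q1-Q4 answer is affected, and the primary analysis is untouched. Severity: minor.

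**What to change.** **SAP 9.9**

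- List the audited sites and calendar months.
- Restore the protocol's models with a random site effect and calendar-time effects: a normal linear mixed model for the interval, and a binomial or count model for number presenting.
- Use births in the audited months as the denominator for number presenting. This is an addition, since the protocol gives none.
- Count each woman once if forms repeat. If the Appendix 5 form is the source this matters, because it tells staff that "we would rather have multiple reports for the same woman than miss episodes of RFM". The form carries an identifier, so duplicates could be removed before anonymised forms are sent for analysis.
- If the audit has no control-phase months, or too few months to adjust for time, state the departure from protocol 8.2 and its reason. Label the tables descriptive, with no intervention effect to be inferred.

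The cost is SAP wording, a list of sites and months, and birth counts for those months. The fallback costs a sentence or two.

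**SAP 9.8 (optional)**

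- Add Apgar below 4, Apgar below 7 and resuscitation to the SAP 9.6 model list.
- Keep the crude tables, labelled as description.

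The cost is three more fits of an existing model on routine data already being collected. There would be three more secondary comparisons without multiplicity control: counting 9.6.4 as four outcomes, the modelled secondary outcomes rise from 22 (19 binary, 3 continuous) to 25. The adjusted intervals would be wider than crude ones, by the factor shown above.

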**9.9.1 Discrete - Number of women presenting with decreased fetal movements**

**9.9.2 Continuous - Interval between perceiving fetal movements and presenting to hospital**

## **9.10 Exploratory Analyses**

Associations between intervention effects on outcomes will be investigated:

- Change in stillbirth rate; and change in the rate of inductions at or above 37 weeks gestation

- Change in stillbirth rate; and change in proportion of babies undelivered by 40 weeks + 0 days who are less than the 10th centile in birthweight

Associations will be presented graphically using one data point for each study site; where feasible a correlation summarising the association will also be calculated.

### **9.11 Adverse Events**

No other adverse event reporting will be undertaken

## **10 Data Sharing**

A set of files containing the analysis code will be prepared. These will be stored alongside the analysis data set in the National Safe Haven.

